# **Clinical Queries**

Clinical queries should be directed to Chief Investigator who will direct the query to the appropriate person

# **Funder**

NIHR Imperial BRC/ Imperial Charity- Research Fellowship

This protocol describes the study and provides information about procedures for entering participants. Every care was taken in its drafting, but corrections or amendments may be necessary. These will be circulated to investigators in the study. Problems relating to this study should be referred, in the first instance, to the Chief Investigator.

This study will adhere to the principles outlined in the NHS Research Governance Framework for Health and Social Care (2nd edition). It will be conducted in compliance with the protocol, the Data Protection Act and other regulatory requirements as appropriate.

# **GLOSSARY OF ABBREVIATIONS**

COPD	Chronic Obstructive Pulmonary Disease
PR	Pulmonary Rehabilitation
LTOT	Long Term Oxygen Therapy
SpO 2	Oxygen Saturations
BTS	British Thoracic Society
CRQ	Chronic Respiratory Questionnaire
CAT	COPD Assessment Tool
HAD	Hospital Anxiety and Depression score
6MWT	6 Minute Walk Test
6MWD	6 Minute Walk distance

# **KEYWORDS**

COPD, Ambulatory Oxygen, Pulmonary Rehabilitation

# **STUDY SUMMARY**

TITLE The Role of Ambulatory Oxygen in Improving the Effectiveness of Pulmonary Rehabilitation for COPD patients

**DESIGN** Single Blinded Randomised Controlled Trial

AIMS Assess the effects of ambulatory oxygen on outcomes from Pulmonary

Rehabilitation

OUTCOME MEASURES 6 Minute Walk Distance, Muscle strength, Dyspnoea, Quality of life

questionnaires, anxiety and Depression score

**POPULATION** COPD patients only

**ELIGIBILITY** COPD patients between the age of 35-85, eligible for PR and who desaturate

on exercise

**DURATION** 1 year

# 1. INTRODUCTION

#### 1.1 BACKGROUND

Pulmonary rehabilitation (PR) is recognized as a core component of the management of patients with COPD (1) and has been clearly demonstrated to improve exercise capacity, reduce dyspnoea and improve quality of life. Although the benefits of PR in COPD are well established there remain a number of unanswered questions regarding how to maximise performance during PR, including the use of ambulatory oxygen. Studies investigating the effects of oxygen use during PR have had conflicting results with one study finding no benefit (2), while another study did report improved walking distance in patients administered oxygen (3). This latter study is used to justify the use of oxygen in PR programmes but the assessment was carried out while breathing the gas to which patients were randomised so it remains unknown if this was an acute effect of the oxygen or a true training effect. Limitations of these studies include inclusion of patients on LTOT, use of a standard oxygen flow rate rather than targeting to correct hypoxemia, limited outcome measures and short term follow-up. It is not known if short term improvements in exercise capacity translate into increased activity after patients complete PR. More sophisticated methods of measuring activity using pedometers are now available that can be used to assess whether oxygen during PR improves activity. Current practice appears to be moving towards administration of oxygen to COPD patients with exercise-induced desaturation during PR despite the lack of evidence that this has any benefits. In addition patients may be given ambulatory oxygen to use long term after completing PR, however it is not known whether patients continue to use oxygen as studies have shown that use of ambulatory oxygen in their home environments is generally poor (4). This has considerable cost implications due both to the direct costs of providing oxygen and the staff time required assessing patients. This lack of evidence is recognised in the British Thoracic Society (BTS) guidelines on PR(1). The guidelines state that 'Supplemental oxygen during pulmonary rehabilitation should be offered to those who fulfil the assessment criteria for long term or ambulatory oxygen unless there are compelling clinical reasons to use alternative criteria.' However the evidence level for this recommendation is Grade D which is the weakest level of evidence. Therefore it remains unknown whether oxygen improves outcomes in PR in COPD patients with exercise-induced desaturation.

## 1.2 RATIONALE FOR CURRENT STUDY

As described in the previous section the evidence base for the use of oxygen in PR is very limited. In the BTS guideline on PR it is stated that the one study that showed benefit for oxygen 'carried a significant risk of bias that influenced its findings. Therefore its results require replication before they can be widely applied', and that 'Supplemental oxygen may be of benefit in selected individuals, but there is currently little information to inform this choice.' Therefore further studies are needed to assess the effects of oxygen on outcomes from PR to justify its cost this. More sophisticated methods of measuring activity using pedometers are now available that were not available in previous studies of oxygen during PR. Therefore the rationale for the current study is to investigate the use of oxygen in COPD patient undergoing PR using a more robust study design and improved methods of assessing exercise capacity.

# 2. STUDY OBJECTIVES

The aims of this study are to

- 1. Assess the effects of oxygen on outcomes from PR.
- 2. Assess how many patients wish to continue to use ambulatory oxygen.
- 3. Assess the usage of ambulatory oxygen following completion of PR.

The hypothesis is that use of oxygen in selected patients improves exercise capacity during PR. The measurable aims will be exercise capacity and on-going usage of oxygen in this patient group.

#### **Primary Objective**

Assess the effects of ambulatory oxygen on outcomes from Pulmonary Rehabilitation

## **Secondary Objectives**

- 1. Assess the proportion of patients that wish to continue to use ambulatory oxygen.
- 2. Assess the usage of ambulatory oxygen following completion of Pulmonary Rehabilitation
- 3. Assess whether initiation of ambulatory oxygen before or after PR has any influence on adherence to usage at 8 and 12 weeks.

# 3. STUDY DESIGN

The study will be a randomised, single-blinded study comparing oxygen with air in COPD patients undergoing PR. The study subjects will be patients with a confirmed diagnosis of COPD who have been accepted for PR and who are not hypoxemic at rest, but have exercise-induced desaturation (defined as a fall in SaO₂ of ≥4% to at least <90%, or any fall to a SaO₂ <90%) and demonstrate positive improvement with use of ambulatory oxygen as per the British Thoracic Society 2015 Home Oxygen Guidelines. It is standard practice for patients to have this assessment prior to commencing PR and as part of the assessment the flow rate required to increase the SaO₂ to >90% during exercise will be determined. Patients will be recruited from PR programs at Imperial College Healthcare NHS Trust Hospital Sites. 20 patients are required in each group to detect a 30% effect size on the 6 minute walk test (6MWT) with 80% power at the 5% significance level and 29 patients in each group to detect a 25% effect with 80% power (5). Therefore a minimum of 20 patients per group will be included.

Baseline assessments prior to commencing PR will include symptom and quality of life assessments including Borg scale for assessment of breathlessness, Chronic Respiratory Questionnaire (CRQ), COPD Assessment Tool (CAT) and the Hospital Anxiety and Depression score (HAD); a 6MWT to measure exercise capacity and Handheld dynamometer to measure muscle strength. In addition we will measure activity at home during and after PR using pedometers as this has never been investigated previously. A yamax Digi-walker SW-200 pedometer will be used to count the number of steps taken per day. Patients will be instructed to wear the device on left side of the body all the time, except when sleeping or showering. Pedometer placement was standardised by placing it on the belt or waistband, in the midline of the thigh, consistent with the manufacturers recommendation and with other studies conducted previously (6, 7). Patients will be record daily step counts on daily diary cards until their final follow up. The subjects will be randomised to receive either oxygen at the flow rate determined at the initial assessment to a maximum flow rate of 6 litres per minute, or room air. The subjects will then undergo a standard program of PR over 6 – 8 weeks and then undergo reassessment. The measures of exercise capacity at the follow up assessment will be carried out off oxygen and will be carried out by an observer blinded as to whether they received oxygen or not during PR. All patients will be provided with ambulatory oxygen for domiciliary after completing PR. All patients will have repeat assessments at 8 and 12 weeks after completion of PR. At these visits data will also be collected on activity, number of exacerbations and hospitalisations and on-going usage of ambulatory oxygen.

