#### 4.2 INCLUSION CRITERIA

- 1) A confirmed diagnosis of Chronic Obstructive Pulmonary Disease (COPD)
- 2) Fulfil the clinical criteria for Pulmonary Rehabilitation (PR)
- 3) Demonstrate exercise-induced desaturation (defined as a fall in  $SaO_2 \ge 4\%$  to at least <90%, or any fall to a  $SaO_2 < 90\%$ ) and demonstrate positive improvement with use of ambulatory oxygen as per the British Thoracic Society 2015 Oxygen Guidelines

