#### 4.3 EXCLUSION CRITERIA

- 1) Use of long term oxygen therapy
- 2) Unable to provide informed consent
- 3) Significant respiratory disease other than COPD
- 4) Any patient needing more than 6 litres per minute oxygen to correct desaturation
- 5) Severe desaturation: SaO2 < 80% during 6 Minute Walk Test
- 6) Any absolute contraindication to Pulmonary Rehabilitation

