## 4.4 WITHDRAWAL CRITERIA

Standard clinical practice criteria for PR will be used, as per BTS PR guidelines.

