# 7. STATISTICS AND DATA ANALYSIS

20 patients are required in each group to detect a 30% effect size on the 6MWT with 80% power at the 5% significance level and 29 patients in each group to detect a 25% effect with 80% power. Therefore a minimum of 20 patients per group will be included. The following statistical methods will be used for data analysis – T test, ANOVA and test for correlation between variables

Data and all appropriate documentation will be stored for a minimum of 10 years after the completion of the study, including the follow-up period.

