#### 8.2 CONSENT

Consent to enter the study must be sought from each participant only after a full explanation has been given, an information leaflet offered and time allowed for consideration. Signed participant consent should be obtained. The right of the participant to refuse to participate without giving reasons must be respected. After the participant has entered the study the clinician remains free to give alternative treatment to that specified in the protocol at any stage if he/she feels it is in the participant's best interest, but the reasons for doing so should be

recorded. In these cases the participants remain within the study for the purposes of followup and data analysis. All participants are free to withdraw at any time from the protocol treatment without giving reasons and without prejudicing further treatment.

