#### 8.5 SPONSOR

Imperial College Healthcare NHS Trust will act as the main Sponsor for this study. Delegated responsibilities will be assigned to the NHS trusts taking part in this study.

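### Does leaving the age range and the resting-oxygen condition out of the Section 4 entry lists change who the trial studies?

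*Combined protocol and SAP*

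**What the plan says.** The Study Summary gives eligibility as "COPD patients between the age of 35-85, eligible for PR and who desaturate" on exercise. Section 3 adds a resting condition: subjects are those "who are not hypoxemic at rest, but have exercise-induced desaturation". It puts no number on resting hypoxemia. Its figures concern the saturation reached on exercise (below 90%) and the level that oxygen should restore during exercise (above 90%).

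Section 4.2 lists three inclusion criteria: confirmed COPD, meeting the clinical criteria for pulmonary rehabilitation (PR), and the third, which begins "Demonstrate exercise-induced desaturation (defined as a fall in". That third criterion accepts either a fall of at least 4% that ends below 90%, or any fall that ends below 90%. It also requires improvement on ambulatory oxygen under a cited guideline. Section 4.3 lists six exclusions. Two bear on oxygenation: "Use of long term oxygen therapy", and a saturation below 80% during the walk test. Section 4.1 lists only the walk test as an evaluation before registration.

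On what happens after entry, Section 4.4 says "Standard clinical practice criteria for PR will be used, as per BTS PR guidelines". Section 8.2 covers patients whose clinician changes their treatment: "In these cases the participants remain within the study for the purposes of followup" and analysis. Section 7 names the methods as "T test, ANOVA and test for correlation between variables" and defines no analysis population.

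**The concern.** Recruiting staff normally work from the inclusion and exclusion lists. If two conditions that define the population are missing from those lists, a patient can satisfy Section 4 and still fall outside the Study Summary or Section 3. Such a patient might be randomised before anyone noticed. Whether to keep that patient in the analysis would then be decided after allocation, in a trial that may have only 20 patients per arm. A reader of the results could also be unsure which population had been studied. That matters here because the Background section criticises previous trials partly for whom they enrolled, namely patients on long term oxygen.

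**Working it through.** The protocol gives no figure to reproduce on this point. The check compares the sections and then works through the saturation rules.

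**1. Where each condition appears**

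| Condition | Study Summary | Section 3 | Section 4.1 | Sections 4.2 and 4.3 |
|---|---|---|---|---|
| Age 35 to 85 | stated | absent | absent | absent from all 9 |
| Resting oxygenation | absent | stated, no number | absent | absent from all 9 |

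**2. Age.** A patient aged 34 or 86 can meet all nine criteria and lie outside the Study Summary's range. This needs no assumption about thresholds.

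**3. Resting saturation.** Let *r* be the resting value and *e* the lowest value in the walk test, both whole numbers. Section 4.3 requires *e* ≥ 80. The second half of the desaturation definition can be read in two ways.

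- *Reading A: a fall may start from any level.* The rule is *e* < *r* and *e* < 90. For *r* below 90, the admitted *e* run from 80 to *r* − 1, which is *r* − 80 values. This gives 0 at *r* = 80, then 1 at 81, rising to 9 at 89. Nine resting values (81 to 89) can pass, each with a fall as small as 1 point.
- *Reading B: the fall must cross 90% from above.* A patient resting below 90% can then enter only through the 4% half, so *r* − *e* ≥ 4 with *e* ≥ 80, which requires *r* ≥ 84. The admitted *e* run from 80 to *r* − 4, which is *r* − 83 values: 1, 2, 3, 4, 5 and 6 for *r* = 84 to 89. Six resting values can pass, with 1 + 2 + 3 + 4 + 5 + 6 = 21 pairs in all.

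Under either reading, Section 4's saturation limits can admit some patients resting below 90%. Whether Section 3 would call them hypoxemic at rest is an inference, because it sets no resting limit.

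**4. Is the 4% half redundant?** Under Reading A it is, since every pair that meets it also meets the other half. Under Reading B it is not, since the 21 pairs enter through it alone. Deleting it could therefore change who qualifies.

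**5. Consequence.** One affected patient is 1/20 = 5% of an arm at the minimum size, or 1/29 = 3.4% at the larger size in Section 7. That is the weight of any patient, and the documents do not show how many would be affected. The sample size statement rests on the size of effect on the walk test, the power and the significance level; neither age nor resting saturation enters it.

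**The case for a change.** The strongest case for acting is that the age gap needs no assumption and the resting gap survives both readings of the desaturation rule. The long term oxygen exclusion does not close the resting gap, because it removes current users and not untreated patients with low resting saturation. The walk-test exclusion concerns exercise values. Correcting the text would take a few lines and no extra visit.

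The omission itself stands. Four things limit its weight.

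- It is an omission from one list and not a contradiction. Nothing says that Section 4 is exhaustive, and a team following the whole protocol would apply the age range and the resting condition as well.
- The nine criteria refer to PR criteria and an oxygen guideline that the protocol does not reproduce. These may screen out some of the patients in question, which cannot be checked from the documents. A fall of at least 4% also cannot be judged without a pre-exercise value, and Section 3 describes this assessment as standard before PR. The assessing clinician should therefore have a resting reading to hand.
- The absence of a named analysis population in Section 7 is a separate matter. It would remain if the lists were perfect, so it adds nothing to this concern. Section 8.2 shows an intention to retain patients, although it is written for changes of treatment.
- It could be argued that several teams will work from Section 4, since Section 8.5 says "Delegated responsibilities will be assigned to the NHS trusts taking part in this study". Section 8.1 also provides for more than one trust, but the recruitment text in Section 3 names the hospital sites of a single trust, so this carries little weight.

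**Conclusion.** No change to the plan follows. The age range and the resting condition are stated in the protocol but not carried into Sections 4.2 and 4.3. Read alone, those lists could admit a patient aged 34 or 86. They could also admit one resting at 81% to 89% or at 84% to 89%, depending on how the desaturation rule is read. Those ranges assume whole-number readings. Their conflict with Section 3 further assumes a resting line at 90%, which the protocol does not state.

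The protocol followed as a whole still gives a sound randomised comparison. Any patient who slips through does so before allocation and is as likely to be assigned to one arm as to the other under equal allocation. No effect on bias or power is shown, and the number of such patients is unknown and may be small. Bringing the statements of eligibility into line, with the sponsor defining the resting condition, would be reasonable housekeeping if the text is revised for another reason. The trial's conclusion does not depend on it.

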#### 3.1 STUDY OUTCOME MEASURES

# **Primary Outcome measure**

Exercise capacity measured with the 6 Minute Walk Test (6MWT)

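### The listed analysis does not commit to using the baseline 6MWT in the primary comparison, and the primary visit, which the documents point to as completion of PR, is never labelled

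*Combined protocol and SAP*

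**What the plan says.** Section 3.1 gives the whole primary outcome as "Exercise capacity measured with the 6 Minute Walk Test (6MWT". It names no visit and does not say whether the variable is the final distance or the change from baseline. The secondary list in the same section does not include a later 6MWT.

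Section 3 and Appendix 1 schedule the 6MWT at baseline, at completion of PR, and 8 and 12 weeks later. Section 3 says "All patients will have repeat assessments at 8 and 12 weeks after completion of PR" and also "All patients will be provided with ambulatory oxygen for domiciliary after completing PR". So the two later tests follow the provision of oxygen to both arms. Off-oxygen testing by a blinded observer is stated for follow-up but not for baseline. Section 4.1 separately mentions a 6MWT within the ambulatory oxygen assessment, and its relation to the baseline test in section 3 is not given.

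Section 7 repeats the sample size (20 per group for a 30% effect, 29 for 25%, 80% power, 5% level) and lists "T test, ANOVA and test for correlation between variables". It does not say which visit is tested, whether baseline enters the analysis, or whether the 5% level is one- or two-sided.

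Several places point to completion of PR. The hypothesis reads "The hypothesis is that use of oxygen in selected patients improves exercise capacity during PR", the primary objective is "Assess the effects of ambulatory oxygen on outcomes from Pulmonary Rehabilitation", and the comparison is described as "comparing oxygen with air in COPD patients undergoing PR". The only objective that names 8 and 12 weeks is about adherence: "Assess whether initiation of ambulatory oxygen before or after PR has any influence on adherence to usage at 8 and 12 weeks".

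**The concern.** The trial is small, and walking distance usually differs more between patients than one programme changes it. In that setting the baseline value is the obvious source of extra precision, and this trial already collects it. A bare t test leaves two choices open: final values, which ignore baseline, or change scores, which over-correct when the correlation is low. The two can differ a good deal in power, and the choice could be made after the data are seen.

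The unlabelled visit is a second, smaller gap. At completion of PR, the between-group difference answers the trial's own question, oxygen against air during PR. At 8 and 12 weeks both arms have been provided with oxygen, so the difference concerns durability, or oxygen started during PR against oxygen started afterwards. Off-oxygen testing removes the acute effect of the gas on the test, but not any effect of weeks of available home oxygen. An ANOVA over all visits would mix the two questions.

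**Working it through.** **1. The plan's own figure.** No mean or standard deviation is given, so 20 and 29 per group cannot be derived directly. They do agree with each other. With n = 2(1.960 + 0.842)² × (CV/effect)² and an assumed coefficient of variation (CV) of 0.336:
- 30% effect: 15.70 × (0.336/0.30)² = 19.7, so 20.
- 25% effect: 15.70 × (0.336/0.25)² = 28.4, so 29.

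Any CV from about 0.334 to 0.3385 gives both figures under the two-sided normal approximation. The percentages are therefore relative to the mean. As standardised effects of 0.30 and 0.25 they would need 175 and 252 per group.

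**2. Anchor for the comparison.** With 20 per arm, a two-sided 5% t test on final values (38 degrees of freedom) has 80% power at a standardised difference d = 0.909. All methods below face this same true effect.

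**3. Effective standardised difference**, with ρ the correlation between baseline and follow-up 6MWD, equal variances and randomised groups:
- final value: d
- change score: d / √(2(1 − ρ))
- ANCOVA: d / √(1 − ρ²), with 37 degrees of freedom and a small further loss for estimating the slope.

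For example, at ρ = 0.3 the change score gives 0.909/√1.4 = 0.768 and ANCOVA 0.909/√0.91 = 0.953. At ρ = 0.7 they give 0.909/√0.6 = 1.174 and 0.909/√0.51 = 1.273.

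**4. Power with 20 per arm** (noncentral t for the first two methods; simulation for ANCOVA, including the slope loss). The last column is the width of the ANCOVA confidence interval divided by that of the final-value interval.

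| ρ (assumed) | Final-value t | Change-score t | ANCOVA | Width ratio |
|---|---|---|---|---|
| 0 | 80% | 51% | 79% | 1.01 |
| 0.3 | 80% | 66% | 82.5% | 0.97 |
| 0.5 | 80% | 80% | 89% | 0.88 |
| 0.7 | 80% | 95% | 97% | 0.72 |

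ANCOVA breaks even with the final-value test between ρ = 0.1 (79.3% against 80.0%) and ρ = 0.2 (80.7% against 80.1%). Its simulated null error is 4.9 to 5.2%.

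**5. Error rate and choice of visit.** With one prespecified visit, or one overall between-group test, the rate is 5%. If any of the three post-baseline visits could carry the claim at an unadjusted 5%, simulation with 20 per arm gives 12.5%, 10.9%, 8.5% and 7.4% at assumed between-visit correlations of 0.5, 0.7, 0.9 and 0.95.

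**The case against.** The strongest reply on the visit is that no careful reader would choose anything but completion of PR. Section 3 describes a reassessment directly after PR, sets the off-oxygen and blinded-observer conditions there, and only then introduces the repeat assessments. Section 6 calls the later visits additional. The hypothesis, primary objective and description of the comparison agree. This largely stands: what is missing is a label, and there are no competing definitions. A reader might infer that the plan lets any of three visits count and so runs a 7 to 13% false-positive rate. The documents do not support that. They name one primary outcome, and no passage states an any-visit rule. Nor do they rule one out, and section 1.1 criticises earlier studies for short follow-up, so a later visit could be defended from the same text.

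On the analysis, section 7 does not exclude ANCOVA, and its t test may have been meant for change scores. Both points stand. A reader might infer that baseline adjustment is worth 17 points of power (80% to 97%). That holds only at ρ = 0.7 and only against a final-value test; against a change score the gain there is 2 points. Nor do the documents show that the planned 80% rested on an unadjusted final-value standard deviation. What remains is that ANCOVA matches or beats both alternatives at every assumed correlation from 0.2 upwards, and the plan commits to none of the three.

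**Conclusion.** The point holds as a gap in prespecification with a worthwhile gain available. The primary comparison should use the baseline 6MWT, and the primary visit should be named.

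At assumed correlations of 0.3, 0.5 and 0.7, ANCOVA gains about 3, 9 and 17 points over a final-value t test, and about 17, 9 and 2 points over a change-score t test. The most it loses is about 1 point, against the final-value test, when the correlation is near zero. These figures rest on assumed correlations, equal variances, 20 per arm, a two-sided 5% level, and an effect set to give 80% power with final values. The documents give no correlation or standard deviation.

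The missing visit label matters less. On the natural reading the error rate is 5%, and the inflated rates are conditional on a rule the plan does not contain. The absence of a multiplicity rule is a consequence of the missing label, not a separate defect.

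**What to change.** In section 3.1, define the primary outcome as 6MWD at completion of PR, measured off oxygen by the blinded observer.

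In section 7, state that:
- the primary analysis compares the randomised groups on that value by ANCOVA adjusted for the pre-PR baseline 6MWD described in section 3;
- the 5% level is one- or two-sided, which sections 3 and 7 leave open (the figures here take it as two-sided);
- 6MWD at 8 and 12 weeks, after oxygen is provided to both arms, is secondary and reported as estimates with 95% confidence intervals.

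Say also whether the baseline test is done off oxygen, and how it relates to the assessment 6MWT in section 4.1, so that the covariate is a single identified measurement.

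Agree this before outcomes are compared by arm. It adds no patient, visit or test and leaves the 20 per group unchanged. The costs are about 1 point of power if baseline and follow-up prove nearly uncorrelated, and that durability cannot be claimed as the primary result, although those data are still collected and reported. The wording does not settle how patients without a 6MWD at completion of PR are handled; that needs its own sentence.
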